1. BACKGROUND AND RATIONALE

1.1 General Introduction

There is potential for severe haze episodes to occur in Singapore, and the main air pollutant in the event of haze is particulate matter (PM). Short-term exposure (continuous exposure to unhealthy daily average PSI levels over a period of a few days) to haze like the pattern seen in Singapore may cause irritation of the eyes, nose, and throat in healthy individuals. Haze particles can also affect the heart and lungs, especially in people who already have chronic heart or lung disease e.g., asthma, chronic obstructive pulmonary disease (COPD), or heart failure.

Haze is a perennial problem in Singapore. Commercially available disposable particulate respirators are typically certified for surgical and occupational use. The test standards are specified according to adult breathing conditions and fit. As commercially available disposable masks designed for occupational use are mainly for adults, such masks do not fit well on children, they do not serve well as protection against Particulate Matter 2.5 (PM 2.5), an air pollutant found in transboundary smoke haze.

Commercially available disposable particulate respirators are typically certified under the NIOSH and CE EN 149:2001+A1:2009 standards for surgical and occupational use. These respiratory masks are tested to filter particulate matter in the air with varying degrees of filtering efficiencies according to the respective categories, e.g. NIOSH KN95 certifies respirators to filter at least 95% of non-oil particulates. The test standards are specified according to adult breathing conditions and fit.

Children's respiratory minute volume and rate are different from adults. As commercially available disposable masks designed for occupational use are mainly for adults, such masks do not fit well on children, they do not serve well as protection against Particulate Matter 2.5 (PM 2.5). As haze is a perennial problem, and there is potential for severe haze episodes to occur again, there is a need to consider the development of disposable particulate respirator with enhanced safety and comfort specific for use in children.

ST Engineering Innosparks Pte. Ltd. developed a new type of disposable particulate respirator (hereon referred to as AIR+ KN95 Mask) that is suitable for use in both adults and children, from ages 7 and above. The masks come in S, M and L sizes, and have been tested according to the KN95 protocol for respirators.

Studies have shown that prolonged wearing of disposable particulate respirators may lead to an increase in carbon dioxide (CO₂) levels in the dead space of the respirator as well as in the re-breathing of the expired air when wearing it. The increased CO₂ levels may result in headaches, increased irritability, and breathing difficulty. In addition, there is some discomfort due to the accumulation of heat and humid air in the dead space of between the respirator and face. However, the mask design is based on our previous AIR+ Smart Mask specifications, which was previously evaluated in a clinical trial performed in collaboration with NUH and the data published in a peer-reviewed journal¹, showing no significant increase in CO₂ retention and the mask was found to be comfortable at rest and on mild exertion. The mask was commercially launched in 2015.

As the masks were developed specifically for school-going children, this study is designed to explore whether the new disposable particulate respirator is safe and effective for use in healthy children aged 7 to 14 years of age. This is through measuring the variation of carbon dioxide levels in children whilst wearing the AIR+ KN95 Mask. End-tidal carbon dioxide pressure (ETCO2) is a good indicator of arterial carbon dioxide pressure (PaCO2) in healthy adults and children and has been used for continuous direct assessment of PaCO2 in clinical contexts. The normal range of PaCO2 is from 35 – 45 mmHg. As there is a slight margin of difference between ETCO2 and PaCO2 values during measurement of about 1.6 +/- 4.3mmHg, this study defines 30 to 50mmHg as the acceptable range for ETCO2 levels.

1.2. Rationale and justification for the Study

a. Rationale for the Study Purpose

Haze is a perennial problem in Singapore. There is a need to consider the development of disposable particulate respirator with enhanced safety and comfort specific for use in children.

ST Engineering Innosparks Pte. Ltd. developed a new type of disposable particulate respirator (AIR+ KN95 Mask) that is suitable for use in both adults and children, from ages 7 and above.

b. Rationale for Doses Selected (not applicable)

No drugs are used in the study.

c. Rationale for Study Population

Commercially available disposable masks designed for occupational use are mainly for adults, such masks do not fit well on children. As the masks under study were developed specifically for school-going children, this study is designed to explore whether the new disposable particulate respirator is safe and effective for use in healthy children aged 7 to 14 years of age.

d. Rationale for Study Design

This study entails the study of subjects doing various activities with and without donning on the mask. The baseline results of subjects without donning on the mask will serve as control.

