11. SAMPLE SIZE AND STATISTICAL METHODS

11.1. Determination of Sample Size

It is anticipated that a child at rest will have a mean ETCO₂ of 40 mmHg with standard deviation of approximately 8 mmHg. Based on the proposed safety threshold of 50mmHg and below for the ETCO₂, an increase of 10 mmHg after the subject wears a mask would indicate non-inferiority. A more stringent tolerance level of 5mmHg in ETCO₂ will be assumed given the variability of the ETCO₂ measurements among the children.

Assuming a one-sided test size of 5% and one-sided power of 80%, at least 80 subjects will be required. To account for the children who may withdraw during the study, a total of 100 children will be recruited, distributed across the age groups.

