11.2. Statistical and Analytical Plans

a. General Considerations

The primary outcome of the study is ETCO₂. The 95% upper confidence limit of the increase in ETCO₂ after wearing a mask will be computed. The proportion and its associated 95% confidence intervals of children whose ETCO₂ are > 50mmHg for at least 3 minutes sustained will also be presented. Similar analysis will be carried out for other physiological parameters such as SPO₂, HR and RR. In addition, the change in mean of visual analogue scale after the child wears the mask will be compared using the paired-t test and adjusted for baseline imbalance using regression analysis.

These analyses will be repeated for physiological parameters collected while at rest and on mild exertion.

b. Safety Analyses

NAD

c. Interim Analyses

This will not be done.

d. Describe the types of statistical interim analyses and stopping guidelines (if any) that are proposed, including their timing.

NAD

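### Unless Figure 1 randomises the order of the unmasked and masked runs, the mask effect on ETCO₂ cannot be separated from the effect of time within the session

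*Combined protocol and SAP*

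**What the plan says.** Section 1.2 d sets out a within-child comparison: "This study entails the study of subjects doing various activities with and without donning on the mask". The comparator is the same child without the mask: "The baseline results of subjects without donning on the mask will serve as control".

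Section 11.1 sizes the study on the same contrast: "an increase of 10 mmHg after the subject wears a mask would indicate non-inferiority". It then tightens the margin: "A more stringent tolerance level of 5mmHg". Section 11.2 a defines the primary estimate: "The 95% upper confidence limit of the increase in ETCO₂ after wearing a mask will be computed". That section repeats the analyses for rest and for mild exertion. It plans a regression adjustment only for the visual analogue scale.

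Random selection is mentioned in 3.1 and 6.1, but only for choosing participants from the eligible pool. No legible section says which condition comes first, whether the order is randomised or counterbalanced, or whether there is a washout. Section 4 refers the reader to Figure 1 in 5.1 for the assessment step, and that figure is not shown in the text reviewed.

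Sections 4 and 6.1 place the mask fit test, which includes deep breathing and bending, before the monitoring equipment goes on. Section 6.1 puts everything in a single day, with a study time of about 50 minutes. On the treadmill, speed is adjusted to a target heart-rate zone and three minutes of steady-state data are then taken.

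**The concern.** A control described as a baseline, together with an outcome described as a rise after the mask, most naturally means unmasked first and masked second for every child. In that order, condition and period are the same variable. Anything that changes ETCO₂ between the first and second run is counted as mask effect: getting used to the nasal cannula, acclimatisation to a test area at 26–32 °C and 50–80% humidity, or wearing-off of the effects of the fit test. On the treadmill, residual warm-up or fatigue is added.

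This is bias, not noise, and more children do not reduce it. A downward drift would help a mask with an unacceptable rise to pass. An upward drift would charge the mask with a rise that it did not cause. The comparison is the basis for a safety statement about children, so the direction of any error matters.

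**Working it through.** **Inputs.** Margin 5 mmHg, one-sided 5%, at least 80 children and SD 8 mmHg, all from 11.1. That SD is the spread between children at rest; the SD of the within-child change is not given. I therefore use three assumed values: 8 mmHg (within-child correlation 0.5), 8 × √2 = 11.3 mmHg (correlation 0) and 5 mmHg (correlation 1 − 25/128 = 0.80). Drift is also an assumption. I read the upper limit in 11.2 a as one-sided 95%, and a pass as that limit lying below 5 mmHg.

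**Step 1: the plan's own figure.** The paired formula is n = [SD × (z₀.₉₅ + z₀.₈₀) / 5]².
- SD 8: [8 × (1.645 + 0.842) / 5]² = 15.8, so 16.
- SD 11.3: 31.7, so 32.
- Two independent groups at one-sided 5%: 4 × 15.83 = 63.3 in total, so 32 per group or 64.
- Two independent groups at one-sided 2.5%: 4 × [8 × (1.960 + 0.842) / 5]² = 80.4, so 41 per group or 82.

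The stated 80 is approached only by the last of these. That mismatch is a separate matter. Here 80 is taken as given.

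**Step 2: what a fixed order estimates.** Let τ be the true mask effect and d the change from first to second run that the mask does not cause. With unmasked first for every child, the mean masked-minus-unmasked difference estimates τ + d. The sample size does not enter the bias.

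**Step 3: false-pass rate at τ = 5 mmHg.** The standard error is SD/√80. To a normal approximation, P(pass) = Φ(−d/SE − 1.645). For SD 8 and d = −1, SE = 0.894 and Φ(1.118 − 1.645) = Φ(−0.527) = 0.299. The noncentral t with 79 degrees of freedom gives:

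| SD of change | SE | d = 0 | d = −1 | d = −2 |
|---|---|---|---|---|
| 5 | 0.559 | 0.050 | 0.551 | 0.971 |
| 8 | 0.894 | 0.050 | 0.296 | 0.716 |
| 11.3 | 1.265 | 0.050 | 0.195 | 0.469 |

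**Step 4: a larger sample.** With n = 100 and SD 8, the rates at d = −1 and −2 are 0.343 and 0.799. The biased answer becomes more certain.

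**Step 5: the other direction.** With τ = 2 mmHg, SD 8 and n = 80, the chance of passing is 0.954 without drift and 0.296 with a drift of +2 mmHg (mean difference 4).

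**Step 6: counterbalanced order.** Unmasked-first children estimate τ + d and masked-first children τ − d. The mean of the two sequence means is τ. A simulation with 40 children per order, SD 8 and drifts of 0, −1, −2 and +2 mmHg gave a false-pass rate of about 5% at τ = 5 and power above 99% at τ = 0. If the order is balanced but the period term is left out, the estimate is still unbiased. A drift of 2 mmHg only raises the SD of the differences from 8 to √(64 + 4) = 8.2.

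**The case against.** The strongest reply is that no sentence fixes the order. Baseline may mean no more than the no-mask reference condition, and section 6.1 says only that different interventions are assessed. The sequence is referred to Figure 1, which is missing from the text reviewed and so cannot be counted as missing from the plan. This stands, and it makes the point conditional.

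A reader might infer that the confounding is established, or that a randomised order in Figure 1 would contradict the text and 11.2. Neither is supported. The text states no order that could be contradicted, and Step 6 shows that a balanced random order leaves the plain paired mean unbiased.

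A reader might also infer that heat, warm-up and fatigue pass wholly into the estimate. The plan has controls against this: a bounded climate, a treadmill speed adjusted to heart rate, and steady-state readings. They reduce these effects without removing them. Fatigue bears mainly on the treadmill contrast. At rest, the condition on which 11.1 is built, the threat is time, acclimatisation and carry-over.

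Finally, the hypothesis in 2.1 is absolute (ETCO₂ within 30 to 50 mmHg), and 11.2 a also reports the proportion sustained above 50 mmHg. Neither is defined as a masked-minus-unmasked contrast, so the point bears on the increase in ETCO₂ and less directly on those two, although drift could still shift absolute values.

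**Conclusion.** The point holds in conditional form. The wording of 1.2 d, 11.1 and 11.2 a implies a fixed unmasked-then-masked order, and no legible section provides a randomised order, a washout or a period term. If the order is fixed, the masked-minus-unmasked contrast is confounded with period, and no analysis or larger sample can undo that. If Figure 1 randomises or counterbalances the order, the charge of confounding falls. What remains is a small gain in precision from a period term, and wording to align.

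The size is illustrative only. At a true rise equal to the 5 mmHg margin with 80 children, drifts of −1 and −2 mmHg give false-pass rates of 30% and 72% (SD of change 8), about 20% and 47% (SD 11.3), or 55% and 97% (SD 5), against a nominal 5%. These rates rest on assumed drifts, an assumed SD of change and a true effect placed exactly at the margin. The documents do not show that any such drift occurs.

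**What to change.** First, state the order of the runs in the text of 5.1 or 6.1, whatever Figure 1 shows.

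If the order is fixed, randomise each child 1:1 to unmasked-first or masked-first, with a short unmasked rest between runs. In 11.2 a, take the one-sided 95% upper limit for the increase in ETCO₂ from a within-child model with a period term, separately for rest and for exertion. In 1.2 d, call the control the unmasked run instead of the baseline.

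If Figure 1 already randomises the order, only the period term and the wording need changing.

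**Cost.** An allocation list and a sentence in 11.2 a, with no extra children, visits or measurements. There are three downsides:
- Staff must follow two sequences.
- A masked-first run may carry over into the control run. The rest between runs is meant to limit this.
- A child withdrawn while masked in the first run would have no unmasked value, so missing data could differ between sequences and relate to the outcome. Such withdrawals should be reported by sequence.

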2. HYPOTHESIS AND OBJECTIVES

2.1. Hypothesis

We hypothesise that the subject's measurements of end-tidal CO2 (ETCO2) levels of using AIR+ KN95 Mask will be within the acceptable range for ETCO2 levels of between 30 to 50mmHg.

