2.2 Primary Objective

The primary objective is to evaluate the physiological impact of AIR+ KN95 Masks on end-tidal carbon dioxide (ETCO2) of children aged 7 to 14 years of age.

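### The only stated hypothesis (masked ETCO2 within 30-50 mmHg) is not the contrast the trial is sized for or analyses first (the within-child increase), and no rule links the two

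*Combined protocol and SAP*

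**What the plan says.** - **Section 1.1** sets the range: "this study defines 30 to 50mmHg as the acceptable range for ETCO2 levels".
- **Section 2.1** makes that range the only hypothesis: masked ETCO2 "will be within the acceptable range for ETCO2 levels of between 30 to 50mmHg". It does not say whether this refers to the group mean, to every child or to a proportion of children.
- **Section 2.2** gives the primary objective as evaluating the mask's effect on ETCO2, without a success criterion.
- **Section 11.1** works with a change. It anticipates, for a child at rest, a "mean ETCO₂ of 40 mmHg with standard deviation of approximately 8 mmHg". It takes 50 mmHg as the safety threshold, says "an increase of 10 mmHg after the subject wears a mask would indicate non-inferiority", and then tightens this: "A more stringent tolerance level of 5mmHg in ETCO₂ will be assumed". The test is one-sided at 5% with 80% power, and at least 80 children are needed.
- **Section 11.2** names ETCO2 as the primary outcome and continues: "The 95% upper confidence limit of the increase in ETCO₂ after wearing a mask will be computed". It then adds the proportion, with its confidence interval, of "children whose ETCO₂ are > 50mmHg for at least 3 minutes sustained will also be presented". All of this is repeated at rest and on mild exertion.

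**The concern.** The hypothesis is about a level, and the powered contrast is about a change. Nothing in the plan connects a result on one to a conclusion on the other.

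Section 11.2 does not say what value the upper limit of the increase must stay below. It sets no acceptable proportion above 50 mmHg. It contains no analysis of the 30-50 range, and the lower bound of 30 is never examined. It does not say whether rest or mild exertion decides.

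Two wrong conclusions are therefore open. The hypothesis could be reported as confirmed because the masked mean lies in range, although the increase exceeds the tolerance used for sizing. Or a small mean increase could be reported as showing that children stay within 30-50 mmHg, which it does not show. The stated one-sided 5% applies to the contrast on the increase and gives no protection to a claim about the level.

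**Working it through.** **The plan's own figure.** Section 11.1 states 80 children. With z = 1.645 + 0.842 = 2.486, margin 5 and no true rise:
- paired, SD of the difference 8: (8 × 2.486 / 5)² = 15.8, so 16;
- paired, SD of the difference 8√2 = 11.3: 31.7, so 32;
- two independent groups: 63.3 in total, so 64 (32 per group).

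None gives 80. The nearest variant is two independent groups at one-sided 2.5% (80.4 unrounded, 82 after rounding per group), which matches neither the stated test size nor the within-child design. That is a separate matter; n = 80 is taken as given below.

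**Inputs.** From 11.1: n = 80, unmasked mean 40, SD 8, tolerance 5, one-sided 5%. Assumed, because the plan does not give them: masked SD 8, correlation within child 0.5 to 0.75, normal values. The SD of the paired difference is 8√(2(1 − r)), which is 8.0 at r = 0.5 and 5.66 at r = 0.75. The one-sided t value on 79 degrees of freedom is 1.664.

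**Reading 2.1 as a group mean.** The plan defines no test for this, so I use the one-sided 95% upper limit of the masked mean against 50.
- The standard error is 8/√80 = 0.894, so the observed masked mean must be below 50 − 1.664 × 0.894 = 48.51.
- The 5 mmHg contrast needs an observed mean rise below 5 − 1.664 × 0.894 = 3.51 (r = 0.5), or below 5 − 1.664 × 0.632 = 3.95 (r = 0.75).

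| True rise (mmHg) | 5 mmHg contrast passes (r = 0.5 / 0.75) | Upper limit of masked mean below 50 |
|---|---|---|
| 3 | 72% / 93% | about 100% |
| 5 | 5% / 5% | about 100% |
| 7 | under 0.1% / under 0.1% | about 95% |
| 8 | about 0% / about 0% | about 72% |

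For example, at a true rise of 7 the masked mean is 47, and (48.51 − 47)/0.894 = 1.69, which gives about 95%. The last column does not depend on the assumed correlation.

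**Reading 2.1 child by child.** These are single values, not the 3-minute sustained endpoint.
- No mask effect: P(above 50) = 1 − Φ(10/8) = 0.106 and P(below 30) = 0.106, so 21% lie outside the range. The chance that all 80 lie inside is 0.789^80, effectively zero.
- True rise 3: P(above 50) = 1 − Φ(7/8) = 0.191 and P(below 30) = Φ(−13/8) = 0.052, so 24% lie outside.

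This reading fails for a mask that does nothing, and it barely separates that mask from one that raises ETCO2 by 3 mmHg.

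**The case against.** **A hierarchy can be inferred.** The upper limit of the increase comes first in 11.2 and matches the sizing, and the proportion is introduced as an addition. This stands as an inference, and the plan should not be read as setting up three equal primary criteria. But no threshold is attached to that limit, and nothing ties it to 2.1.

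**The criteria are related.** Section 11.1 builds its 10 mmHg from the distance between 40 and 50, then tightens it to 5. With an unmasked mean near 40, a rise below 5 keeps the masked mean below about 45, so passing the contrast implies the group-mean reading. This stands. On that reading the conflict runs one way only: 2.1 can be met when the contrast fails, not the reverse.

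**The size of the gap is the difference between 5 and 10.** This also stands. At r = 0.5, testing the rise against 10 would pass in about 95% of trials at a true rise of 7 and in about 72% at 8, the same as the masked-mean reading. A reader might also take the row at a true rise of 5 as evidence that the criteria disagree in about 95% of trials. That row is uninformative, because any 5% test passes 5% of the time at its own margin.

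**The wording of 2.1 leans towards individual measurements.** If so, the hypothesis would almost never be confirmed at SD 8, and the case of a confirmed hypothesis beside a failed contrast all but disappears. What remains is a hypothesis that fails whatever the mask does.

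**The study is described as exploratory.** That bears on how serious the point is. But 11.1 uses non-inferiority, a test size and power, and these need a stated rule.

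**Conclusion.** The mismatch is real: the one hypothesis is neither the contrast that was sized nor one that 11.2 analyses, and the choice of criterion can change the conclusion.

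Under the group-mean reading, a true rise of 7 mmHg meets 2.1 in about 95% of trials and passes the 5 mmHg contrast in under 0.1%. This rests on n = 80, an unmasked mean of 40, masked SD 8, correlation 0.5 to 0.75, and a masked-mean criterion that the plan does not itself specify. It arises because 40 leaves 10 mmHg of headroom against a tolerance of 5. Under the child-level reading, about 21% of single values fall outside 30-50 with no mask effect.

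Two stronger inferences are not supported. One is that the same data could confirm 2.1 and fail the contrast on any reading; at SD 8 this needs the group-mean reading. The other is that the 19% above 50, or the 24% outside the range, at a rise of 3 measures harm from the mask. Most of it comes from the assumed SD, and the plan counts only values sustained above 50 mmHg for at least 3 minutes.

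**What to change.** 1. **Section 2.1:** restate the primary hypothesis as the mean within-child increase in ETCO2 (mask minus no mask) at rest being below the 5 mmHg tolerance in 11.1. Rest is the condition for which 11.1 gives its mean and SD. Naming it matters: without it, two contrasts still compete.
2. **Section 11.2:** state that the primary analysis is the one-sided 95% upper confidence limit of that mean increase, and that the hypothesis is supported only if the limit is below 5 mmHg.
3. **Section 11.2:** list as secondary, each with and without the mask where measured: the same contrast on mild exertion, the proportion above 50 mmHg for at least 3 minutes, and the proportion within 30-50 mmHg. State that none can replace a failed primary contrast.
4. **Section 11.2:** state that a passing mean increase does not show that individual children stay within 30-50 mmHg.

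These are wording changes, with no new children, visits or measurements. The cost is that lying within 30-50 mmHg is no longer a success claim on its own, so the conclusion is narrower.
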